6.3.1.12 Laboratory Variables

Laboratory assessments will be performed locally at each center's laboratory by means of their established methods. Before starting the study, the Investigator will supply IQVIA/Sponsor with a list of the normal ranges and units of measurement.

The laboratory variables that will be assessed in accordance with the schedule of procedures described in Table 1 are summarized in Table 3.

The Investigator must review Screening laboratory results for patient eligibility prior to enrolling.

Laboratory tests can be repeated earlier than the next scheduled consecutive study visit at the Investigator's discretion and any associated safety issue should be followed up as per the Investigator's clinical judgment until resolution/stabilization.

In the event that the laboratory parameters show a significant shift from baseline values, patients will then be scheduled for an interim visit within 2 weeks to repeat the laboratory measurements.

Table 3: Laboratory Assessment

Hematology:	RBC count MCV MCH Leucocyte differential count Blasts Promyelocytes Myelocytes Metamyelocytes Band Neutrophils Segmented Neutrophils Eosinophils Basophils Lymphocytes Monocytes Platelets WBC count Hemoglobin Hematocrit	Urinalysis:	pH Protein Glucose Ketone Bilirubin Blood Leukocyte esterase Nitrite
Coagulation	INR aPTT		
Clinical Chemistry:	Albumin Creatinine Calcium Glucose Triglycerides Urea Uric acid Cholesterol HgbA1c Potassium Sodium Alkaline phosphatase GGT AST ALT Total bilirubin	Bone Marrow Aspiration	Aspiration site Cellularity Blasts Promyelocytes Myelocytes + Metamyelocytes Band + Segment Erythroid series Mono-histiocytes Eosinophils Plasma cells Lymphoid cells Miscellaneous Auer rods Dysplastic change Cytochemical
Serology*:	HIV HBsAg HBV DNA if positive HBsAg HCV antibody		
Pregnancy Test:	Serum or urine pregnancy test will be performed at the Screening and end of treatment visits for all females except those surgically sterile or 2 years postmenopausal. Subsequent serum or urine pregnancy tests are allowed at the Investigator's discretion.		

Abbreviations: ALT = Alanine aminotransferase; AST = Aspartate aminotransferase; aPTT= activated partial; thromboplastin; DNA = deoxyribonucleic acid; GGT = Gamma glutamyl transferase; HCV = Hepatitis C virus; Hemoglobin A1c = HgbA1c; HBsAg = Hepatitis B surface antigen; HBV= hepatitis B virus; HIV = Human immunodeficiency virus; INR = international normalized ration; MCH = Mean corpuscular hemoglobin; MCV = Mean corpuscular volume, time; WBC = white blood cells; RBC = red blood cells.

* If HBsAg result indicate active infection then test HBV DNA.

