1.4 Clinical Experience with ASLAN003

ASLAN003 has been administered to healthy subjects in 3 Phase I studies.

The safety, tolerability and PKs of ASLAN003 and its metabolites have been evaluated in healthy male subjects following oral administration of single ascending doses of 1, 2, 5, 10, 25, 50 and 100 mg (7 dose levels) of ASLAN003 in healthy male Caucasian subjects in a Phase I study (*Study M/186323/01*). Although $t_{1/2}$ was consistent across the different dose levels, C_{max} and AUC increased less proportionally with increasing dose. The main metabolite circulating in plasma was LAS186558 with mean AUC values across all administered doses between 3.4% and 9.8% of the mean AUC values of the parent drug; metabolite. LAS186876 was a minor metabolite and was formed at less than 2% of parent drug AUC. ASLAN003 was well-tolerated at all doses studied.

In another Phase I, randomized, double-blind, placebo-controlled, 2-part study (*Study ASLAN003-001*), the safety, tolerability and PKs of single ascending doses (SAD) and multiple ascending doses (MAD) of ASLAN003 were evaluated in healthy Asian subjects. ASLAN003 administered as single and multiple doses of 100 mg, 200 mg, and 400 mg under fed and fasted conditions safe and well-tolerated in healthy subjects. For ASLAN003 and its 2 oxidative plasma metabolites, there was no evidence of departures from dose proportionality following a single dose under fasted conditions in terms of area under the curve from time 0 extrapolated to infinite time ($AUC_{(0-inf)}$), whereas the analyses revealed less dose proportional increase in C_{max} .

Following a single oral dose of 200 mg ASLAN003 with a high-fat meal (fed state), the median t_{max} was delayed by 1.5 hours as compared to the 200 mg dose in the fasted state. The C_{max} and AUC of ASLAN003 were increased by 29% and 18% respectively and inter-subject variability was reduced. Mean $t_{1/2}$ was similar under both fed and fasted dosing conditions for both parent drug and the 2 metabolites.

In the MAD part of the study (100 mg, 200 mg, and 400 mg, QD for 7 days), the plasma AUC_{tau} and C_{max} for ASLAN003 and LAS186876 revealed no evidence of departures from dose proportionality with increasing doses of ASLAN003 when taken after a meal. However, the AUC_{tau} and C_{max} for LAS186558 increased in a less dose-proportional manner.

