The t_{max} and $t_{1/2}$ for ASLAN003 were dose-independent following QD doses across the selected dose range; 5 and 16 hours, respectively. Steady-state concentrations of ASLAN003, LAS186558, and LAS186876 were achieved by Day 4 across the selected dose range. Following daily repeated dosing, exposure to ASLAN003 and LAS186558 (AUC) appeared to accumulate slightly (less than 30% increase). The exposure was higher in elderly subjects (AUC_{tau}) of ASLAN003 was increased by 53% and C_{max} by 41%), which may be explained by their lower body weight. Renal elimination of free (unconjugated) ASLAN003, LAS186558, and LAS186876 were negligible (<0.8% of the administered dose). Phase II metabolism appeared to be an important route of elimination. Conjugation was most prevalent for ASLAN003 and LAS186558.

Most frequently reported adverse events (AEs) across this ASLAN003-001 study were abnormality in laboratory investigations and included elevated alanine aminotransferase (ALT), aspartate aminotransferase (AST), gamma glutamyltransferase, blood cholesterol increased, blood creatine phosphokinase increased, electrocardiogram (ECG) PR, and blood glucose increased. The safety assessment results reported in patients aged ≥ 55 years were mostly comparable with those of younger subjects other than for greater changes in the laboratory assessments in the elderly subjects compared to the younger subjects, notably the liver function tests.

Another Phase IB study (*Study ASLAN003-002*) evaluated the safety, tolerability and PKs of multiple doses of 100 mg of ASLAN003 QD for 14 days in healthy elderly Asian subjects (age > 55 years old). The study was conducted at a single center in Singapore where 7 of the planned 8 elderly subjects were enrolled into Stage 1 of the study, of which

5 subjects received ASLAN 100 mg QD on Day 1; and 4 of these subjects received ASLAN 100 mg QD on Day 8. Only 1 subject completed 14 days of QD dosing. Stage 2 of the study was not conducted. Following daily repeated dosing, mean plasma exposure to ASLAN003 expressed as $AUC_{(0-24)}$ increased 1.2-fold after multiple dosing on Day 8 compared to a single dose on Day 1. Following repeat QD dosing, the relative systemic exposures to the metabolites LAS186558 and LAS186876 were around 10% and 1%, respectively.

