3.3 Criteria for Evaluation of the Study

3.3.1 Primary Endpoints

Part 1:

The primary objective of determining the optimum monotherapy dose of ASLAN003 in AML patients is based on the following endpoints:

- **Overall Complete Remission Rate (OCRR):** Defined as the proportion of patients with a best response of complete remission (CR) or complete remission with incomplete hematologic recovery (CRi), defined in accordance with the International Working Group (IWG) Response Criteria in AML.
- **Safety and tolerability:** Based on AEs, safety assessments (including vital signs, ECG parameters, clinical laboratory tests) and treatment exposure/dose intensity.

Part 2:

- **OCRR:** defined as described above for *Part 1*.

3.3.2 Secondary Endpoints:

- Efficacy (*Parts 1 and 2*):
 - **Relapse Free Survival (RFS):** Defined as the time the criteria for remission (CR or CRi) are first met until there is evidence of patient relapse, regardless of whether the patient is still taking study drug. Relapse is defined as:
 - The reappearance of leukemic blasts in the peripheral blood or > 5% blasts in the bone marrow not attributable to any other cause;
 - The appearance of new dysplastic changes;
 - The reappearance of or development of cytologically proven extramedullary disease;
 - The reappearance of a cytogenetic or molecular abnormality.

- **Clinical Benefit Rate (CBR):** defined as the proportion of patients with an AML IWG best response of CR, CRi or partial remission (PR).
- % change from baseline in BM blasts at Day 29.
- Safety and tolerability (**Part 2 ONLY**):
 - Based on AEs, safety assessments (including vital signs, electrocardiogram [ECG] parameters, clinical laboratory tests) and treatment exposure/dose intensity.
- Pharmacokinetics (Part 1 ONLY):

If estimable, the following parameters will be calculated on Days 1 and 8, Cycle 1:

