5.3 Permitted Dose Interruptions of Study Drug

If patients experience a CTCAE Grade ≥ 3 toxicity attributed to ASLAN003 by the investigator, the study drug should be interrupted. Patients with Grade ≥ 3 AEs which are associated with underlying disease such as anemia, bone marrow hypocellular, febrile neutropenia, and decreased lymphocyte count, neutrophil count, and platelet count may keep receiving ASLAN003 treatment at investigator's discretion. The study drug should be resumed once the AE recovers to Grade 1 or less. If study drug is interrupted for continuous 28 days due to AE, the patient must be withdrawn from the study drug and recorded as unacceptable toxicity. If upon re-introduction of ASLAN003, a Grade 2 AE of the same event re-occurs, a dose reduction on a case-by-case basis can be implemented upon agreement with the CRO/Sponsor. For Grade ≥ 3 AST, ALT, or GGT elevations, interruption of study drug is based on the assessment of Child-Pugh score (Class A, B or C, refer to Appendix 3) and is demonstrated in Table 2.

Table 2

If Grade 3 AST/ALT/GGT	
Class A: Reduce dose by 50 mg for 1 week then reassess	G4 : Refer to "If Grade G4 AST/ALT/GGT"
	*Class A, still G3: Reduce dose by 50 mg
	*Class A, G2: Maintain current dose
	*Class A, \leq G1: Resume last higher dose
Class B with Grade 1 to 3: Refer to the action of "If Grade 3 AST/ALT/GGT, Class \leq B"	
Class \geq B: Interrupt until \leq G1, then resume original or reduced dose per investigator's discretion	
If Grade 4 AST/ALT/GGT	
Dose interruption, and follow up weekly until \leq G1	Class A: Reduce dose by 50 mg or maintain original dose per investigator's discretion [#]

	Class \geq B Reduce dose by 50 mg [#]
--	---

*Monitor dose every week until back to original dose

[#]Withdrawal if a secondary G4 event is observed

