6.3.6 Additional Safety Assessments

There are no additional safety assessments planned for this study.

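### Table 3 leaves out creatine phosphokinase, the one blood analyte among the frequent adverse events of ASLAN003-001 that this trial does not schedule, so symptom-free rises will not be systematically detected or described by dose

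*Protocol*

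**What the plan says.** Protocol section 1.4 summarises earlier clinical experience. On ASLAN003-001 it states: "Most frequently reported adverse events (AEs) across this ASLAN003-001 study were abnormality in laboratory investigations". The items it then names are ALT, AST and gamma glutamyltransferase, followed by "blood cholesterol increased, blood creatine phosphokinase increased, electrocardiogram (ECG) PR, and blood glucose increased". The same section says that the study was randomized, double-blind and placebo-controlled, and that single and multiple doses "of ASLAN003 were evaluated in healthy Asian subjects".

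The chemistry panel for the present trial is in section 6.3.1.12, Table 3: "Albumin Creatinine Calcium Glucose Triglycerides Urea Uric acid Cholesterol HgbA1c Potassium Sodium Alkaline phosphatase GGT AST ALT Total bilirubin". CPK does not appear there or elsewhere in Table 3. It is also absent from the schedule in Table 1, the visit lists in section 7.2 and the SAP list of tables, listings and figures. Section 6.3.6 adds: "There are no additional safety assessments planned for this study".

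Section 3.3.1 makes safety and tolerability a Part 1 primary endpoint alongside the remission rate, defined as: "Based on AEs, safety assessments (including vital signs, ECG parameters, clinical laboratory tests) and treatment exposure/dose intensity".

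**The concern.** The protocol records a laboratory abnormality as frequently reported in a previous study of this drug, then sets up a safety panel that measures every other blood analyte on the same list. It gives no reason for the difference.

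A CPK rise without symptoms is purely a laboratory finding. If the test is not drawn, no adverse event arises from it, and the tables will show few or no events at any dose whatever the true rate. A reader of the study report could take that as evidence of absence.

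The earlier data are relevant here. ASLAN003-001 used 100, 200 and 400 mg, the same daily range as this trial (100 mg QD up to 200 mg BID, which is 400 mg a day). Its repeat dosing lasted 7 days, whereas dosing here continues in 28-day cycles. Part 1 chooses the dose partly on laboratory safety, so what the panel leaves out is also missing from the evidence for that choice.

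**Working it through.** **Step 1: match the list in section 1.4 to the plan.**

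| Named in section 1.4 | Scheduled in this trial? |
|---|---|
| ALT | Yes, Table 3 |
| AST | Yes, Table 3 |
| Gamma glutamyltransferase | Yes, Table 3 (GGT) |
| Cholesterol | Yes, Table 3 |
| Glucose | Yes, Table 3 |
| ECG PR | Yes, 12-lead ECG in Table 1; PQ interval in SAP 3.2.1 |
| CPK | No |

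Table 3 has 16 chemistry analytes. Six blood analytes are named in section 1.4; five are in the panel and one, CPK, is not.

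**Step 2: who could still contribute.** The design diagram in the synopsis plans 6 patients per cohort and marks the 100 mg QD cohort as completed. Section 1.6 already uses that cohort's PK data.

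- Part 1 with all remaining cohorts: 3 × 6 = 18 patients.
- Part 1 if the optional 200 mg BID cohort is not opened: 2 × 6 = 12 patients.
- Part 2: 20 patients.

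**Step 3: chance of seeing at least one case if CPK is measured.** The documents give no CPK rate, so the true per-patient rate p is an assumption, taken over 10-30%. The formula is P(at least one) = 1 − (1 − p)^n.

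| n | p = 10% | p = 30% |
|---|---|---|
| 6 (one cohort) | 1 − 0.9^6 = 1 − 0.531 = 46.9% | 1 − 0.7^6 = 1 − 0.118 = 88.2% |
| 12 (two cohorts) | 1 − 0.9^12 = 1 − 0.282 = 71.8% | 1 − 0.7^12 = 1 − 0.014 = 98.6% |
| 18 (three cohorts) | 1 − 0.9^18 = 1 − 0.150 = 85.0% | 1 − 0.7^18 = 1 − 0.0016 = 99.8% |
| 20 (Part 2) | 1 − 0.9^20 = 1 − 0.122 = 87.8% | 1 − 0.7^20 = 1 − 0.0008 = 99.9% |

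At a lower assumed rate of 5%, the figures are 26.5% for n = 6 and 64.2% for n = 20.

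**Step 4: compare with the plan as written.** With no scheduled CPK, a symptom-free rise is not seen at any scheduled visit, whatever p is. The plan has no stated figure on this point to reproduce.

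**The case against.** The strongest reply is that section 1.4 supports less than it may seem to.

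- **Strength of the signal.** The list covers a placebo-controlled study in healthy subjects, without arm, incidence, grade, dose relation or causality. Section 1.5, on known or potential risks, names ALT, AST and total bilirubin for monitoring. Section 1.4 calls liver-test elevations a likely class effect. CPK appears in neither statement. The protocol refers to the Investigator's Brochure for detail, and that is not available here. This stands: the documents show a reported finding. A reader might infer an established drug toxicity, and they do not support that.
- **Other routes of capture.** Section 6.3.1.2 requires adverse events to be documented however they are identified, and section 6.3.1.12 says: "Laboratory tests can be repeated earlier than the next scheduled consecutive study visit at the Investigator's discretion". So it would be wrong to infer that CPK rises cannot be detected at all. But this route concerns repeat tests and names no trigger for CPK. Ad hoc values would have no baseline and no common schedule, so they could not describe the dose cohorts.
- **Small numbers.** The study is not powered and plans no formal analysis. With 6 patients per cohort, CPK could only be described. That is true of the whole safety panel and is no reason to omit one analyte.
- **Liver interpretation.** A reader might also infer that AST rises from muscle will be taken for liver toxicity, because section 5.3 says that for Grade 3 or higher AST, ALT or GGT "interruption of study drug is based on the assessment of Child-Pugh score". The documents do not support this. None of them attributes AST rises to muscle, and section 1.3.4 describes a hepatocyte mechanism. ALT, GGT, alkaline phosphatase and total bilirubin are in the same panel. Nothing shows that AST accompanying a CPK rise would reach Grade 3. Nor does an isolated AST rise make a potential Hy's law case, since SAP 7.7.1 also requires total bilirubin above 2 × ULN.

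**Conclusion.** The point holds as a gap in systematic measurement. CPK is the only one of the six blood analytes named in section 1.4 that the trial does not schedule. Symptom-free elevations will go unseen, and the Part 1 co-primary safety assessment will have nothing systematic to say about them by dose.

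The size rests on an assumed rate. At 10-30%, scheduled measurement would show at least one case with probability 47-88% in a cohort of 6, 85-99.8% in 18 remaining Part 1 patients (72-98.6% in 12) and 88-99.9% in Part 2. These figures would apply to any unmeasured analyte at the same rate; they are not an estimate of CPK toxicity.

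A reader might count all 24 Part 1 patients as potential contributors. That is not supported, because the starting-dose cohort is complete and cannot gain these data. Even with the change, the description by dose would lack 100 mg QD.

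This is an inexpensive improvement to the safety data. The plan contradicts no promise of its own, and no dose or management rule is in question.

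**What to change.** Add CPK to the clinical chemistry column of Table 3, prospectively, for the remaining Part 1 cohorts and Part 2. Draw it at the visits where Table 1 already schedules full chemistry: screening, Cycle 1 Days 1, 8, 15 and 22, Day 1 of Cycle 2 and later cycles, and end of treatment. Leave Cycle 1 Day 10 as it is, since Table 1 footnote d limits that draw to AST, ALT and total bilirubin.

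In the SAP, include CPK in the chemistry listing (16.2.8.2) and the chemistry profile and box plots (figures 14.3.4.2, 14.3.4.4 and 14.3.4.7). State that it is not available for the 100 mg QD cohort, so that its absence there is not read as zero events. If the sponsor has a reason for omitting CPK, section 6.3.1.12 should give it.

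The cost is one extra assay on blood already drawn at local laboratories, one line in Table 3, an eCRF field and a line in the SAP. It needs no extra visit, draw or patient. The downside is a small assay cost and some incidental low-grade findings.

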6.3.2 Physical Examinations

Physical examinations will be performed in accordance with the Schedule of Assessments (Table 1).

The Investigator will conduct a complete physical examination in all patients at the Screening Visit and partial physical examination in all patients during subsequent visits. The physical examinations will cover the following general appearance, head, ears, eyes, nose, throat, hair, skin, respiratory, cardiovascular, gastro intestinal, musculoskeletal, hepatic, neurological, and mental status. Clinically relevant physically examination findings during the study will be recorded as AEs. Findings will be recorded in the eCRF.

6.3.3 Vital Signs

The following vital signs will be assessed in accordance with the Schedule of Procedures (Table 1)

- Blood pressure (systolic and diastolic; mmHg);
- Heart rate (beats per minute);
- Body temperature (degree Celsius[°C]);
- Respiration rate (breaths per minute).

Any abnormal findings that are clinically significant, in the opinion of the Investigator, will be recorded as an AE. Vital sign measurements will be recorded in the eCRF.

6.3.4 Electrocardiograms

Standard 12-lead ECGs will be performed in accordance with the Schedule of Procedures (Table 1)

A 12-lead ECG will be performed at screening, the end of investigational therapy, and when clinically indicated by the Investigator. The Investigator or qualified designee is responsible for determining if any change in patient management is needed and must document his/her review of the ECG printed at the time of evaluation.

6.3.5 ECOG Performance Status

ECOG will be evaluated for all patients at Screening, and during all study visits until follow-up. The detailed description of ECOG Status is provided in Appendix 2: ECOG Performance Status.

6.3.6 Additional Safety Assessments

There are no additional safety assessments planned for this study.

6.4 Pharmacokinetics Assessment (Part 1 ONLY)

The blood samples for determination of ASLAN003 and metabolite concentrations will be collected on Day 1 and Day 8 Cycle 1 in Table 4 at the following timepoints:

Table 4: ASLAN003 Pharmacokinetic Assessment Schedule

Scheduled Visit	Time Points (h)	PK Parameters
Day 1	Pre-dose	C_{max} , $C_{max\ ss}$, C_{trough} , t_{max} , AUC_{τ} , $t_{1/2}$, $t_{1/2\ eff}$, Cl/F^* & V_{ss}/F^*
	Post dose: at 1, 2, 4, 5, 6, 8, 12#, and 24 hours	
Day 8	Pre-dose	$C_{max\ ss}$, C_{trough} , $t_{max\ ss}$, $AUC_{\tau\ ss}$, Cl/F^* , $t_{1/2}$, $t_{1/2\ eff}$, $MRAUC^{**}$, MRC_{max}^{**} , $RacAUC$, and $RacC_{max}$
	Post dose: at 1, 2, 4, 5, 6, 8, 12#, and 24 hours	

Note: Only ASLAN003 and its metabolite's (LAS186558) concentrations and PK parameters will be determined in this study.

* Parameter calculated only for ASLAN003

** Parameter calculated only for LAS186558

Sample collected for BID regime only.

Abbreviations: AUC = area under the plasma concentration curve; AUC_{τ} = AUC over the dosing interval; $AUC_{\tau\ ss}$ = AUC_{τ} at steady state; Cl/F = apparent total clearance of the drug from plasma after oral administration at steady state; C_{max} = maximum observed plasma concentration; $C_{max\ ss}$ = C_{max} at steady state; C_{trough} = Trough plasma concentration; $RacAUC$ = accumulation ratio for AUC; $RacC_{max}$ = accumulation ratio for C_{max} ; t_{max} = time corresponding to occurrence of C_{max} ; $t_{max\ ss}$ = time corresponding to occurrence of $C_{max\ ss}$; MR = metabolic ratio; $MRAUC$ = metabolic ratio for AUC; MRC_{max} = metabolic ratio for C_{max} ; $t_{1/2}$ = effective elimination half-life; $t_{1/2\ eff}$ = effective elimination half-life at the steady state; V_{ss}/F = apparent volume of distribution at steady state after oral administration

In BID regime i.e 100mg BID and 200mg BID the PK sampling will be done at following timepoints: pre-dose, 1, 2, 4, 5, 6, 8, and 12 hours (or evening pre-dose). For Part 2- Steering Committee will decide whether PK analysis is required or not and ASLAN pharmaceuticals will be updated accordingly

6.4.1 Collection of Blood Samples

Blood samples for determination of plasma concentrations of ASLAN003 and LAS186558 will be collected from patients according to the PK sampling schedule described in Table 1: Schedule of Study Assessments. Detailed sample collection, label, storage, and shipment processes will be described in the Laboratory Manual. The exact date/time of the blood sample collection will be recorded in the patient's eCRF.

